Study Protocol and Statistical analysis plan

Can Massage During One Year Improve Health in Health-care Providers Working in Hospital

NCT: 05555082

Date: 2025-10-17

Study design.

This study used an embedded mixed methods pre-post design, where qualitative data were collected at the final follow-up to complement and help interpret quantitative finding ¹. A mixed-methods approach combines quantitative and qualitative data to explore a phenomenon more comprehensively, allowing statistical trends (quantitative) to be explained through qualitative insights and qualitative findings to complement or expand quantitative results ¹. The embedded design is flexible and adaptable, making it valuable for complex research questions where both numerical and narrative insights are needed. Quantitative data were prioritized to appraise limited efficacy, defined under Bowen's feasibility framework as a preliminary within group assessment of the direction and magnitude of change, and to assess acceptability indicators including recruitment, adherence, and participant satisfaction ². Qualitative data were collected at 12 months to deepen understanding of participants' experiences ¹. Integration occurred during analysis by comparing qualitative themes with quantitative outcomes to examine convergence and divergence, with details provided in the Results and the Discussion.

Participants

While the literature reviewed in the introduction refers to (HCW) broadly, our sample was limited to registered and assistant nurses. This focus reflects the reality of the inpatient ward setting, where these professionals are most exposed to physically and emotionally demanding conditions, including shift work and close patient contact. Thus, registered and assistant nurses working in a medical ward at a Swedish hospital were eligible to participate in the study. To be included, participants needed to work in patient care at the ward for at least 50% of full-time hours. Approximately 130 nurses were estimated to meet the eligibility criteria, and we planned to recruit 50 nurses. The sample size was pragmatically based on operational capacity and resource availability, for example available funding only allowing us to offer a limited number of massage sessions. In addition, the number was considered reasonable to assess feasibility parameters such as recruitment yield, adherence, and acceptability, in line with Bowen et al. (2009) ². While not statistically powered, the target was selected to support interpretation of feasibility outcomes. Recruitment was scheduled for a one-month period (November–December 2022) before the planned start of the intervention in January 2023. To raise awareness ahead of this short recruitment window, information about the upcoming study was shared with staff during routine staff meetings prior to the formal registration period. Recruitment was then carried out through an advertisement on the clinic's

website and an email sent to all healthcare staff at the clinic. The recruitment email was directed specifically to the clinic's nursing staff, in accordance with internal mailing list structures. Other professional groups, such as physicians, physiotherapists, or social workers, were not contacted and were not eligible to participate. Both the advertisement and the email provided detailed information about the study, including the maximum number of participants (50), and included a link to a registration form for those interested. The form collected participants' names, phone numbers, and email addresses.

Individuals who registered and meet the inclusion criteria were emailed and invited to meet with the research nurse. During the appointment, participants had the opportunity to ask the nurse additional questions about the study and were asked to provide written consent for participation. At the visit baseline measures were obtained, including blood pressure, height, and weight, together with the baseline questionnaires.

The intervention

The participants received classic massage in 30-minute sessions approximately once a month over the course of one year (i.e., 2023). This duration was based on the standard hands-on treatment time offered by the certified massage therapists contracted for the study. Massage sessions were scheduled outside of working hours in agreement between each participant and the therapist and took place in a quiet and private room at a massage clinic to support relaxation.

Two certified massage therapists were engaged for the study, and participants were evenly divided between them. Each participant received all their sessions from the same therapist to promote continuity and individual adaptation of the treatment. Both therapists were certified in classic Swedish massage and had 15 and 21 years of experience operating private massage practices. The treatment followed the principles of classic massage, including kneading, gliding, and tapping techniques, and primarily targeted areas commonly affected by work-related strain, such as the back, shoulders, and neck. The depth and focus of the massage were tailored to individual needs through ongoing dialogue with each participant. Because ward operations and summer vacations were expected to potentially reduce availability in June and July, the protocol allowed rescheduling across adjacent months; no blanket pause was planned. The target total exposure per participant was 10 to 12 sessions within twelve months, depending on individual scheduling. No exclusion criteria were set based on exact month-to-month spacing.

Data collection

Data was collected at three time points: baseline, 6 months, and at the end of the massage intervention after 12 months. Baseline data were collected at the initial appointment with the research nurse. Prior to this appointment, participants received a package of questionnaires to complete at home, which they returned during the visit. This procedure allowed participants time to reflect on the questions while ensuring that the completed forms could be checked for completeness or clarified during the appointment. These questionnaires covered background variables and outcome variables of interest (i.e., stress, mental health, sleeping problems, physical activity, HR-QoL and work ability). Participants were provided with a stamped envelope to return the completed questionnaires, either by handing them to the research nurse or by mailing them to the project leaders at the clinic, PJ or LE. At the 6-month follow-up, participants completed the same set of questionnaires as at baseline which included questions about the number of massage sessions they attended, as well as questions about stress, mental health, sleep problems, HR-QoL, and work ability. At the end of the intervention at 12 months (December 2023–January 2024), participants again completed the same set of questionnaires, along with additional items on physical activity, satisfaction, and open-ended questions. On this occasion, they also rated their physical activity and scored their satisfaction with the massage on a scale, as well as responded to open-ended questions, allowing for the collection of both quantitative and qualitative data at 12 months-follow-up.

Feasibility outcomes

Limited efficacy

The quantitative outcome measures were collected to explore such early signals of effect, assess the relevance and sensitivity of the instruments used, and inform the design of a future fully powered trial. This does not imply low effectiveness, but rather a structured exploration of whether further testing is warranted ².

Quantitative data collection

Stress

Stress levels were evaluated using the Perceived Stress Scale-10 (PSS-10)³. The questionnaire consists of 10 items that assess how unpredictable, uncontrollable, and overloaded respondents find their lives. Participants rate each item on a 5-point Likert scale, ranging from 0 (never) to 4 (very often), reflecting their feelings and thoughts during the past month. The scores for the PSS-10 range from 0 to 40, with higher scores indicating higher

perceived stress. The PSS-10 has been validated in Swedish and is considered a reliable indicator of perceived stress ⁴.

Mental Health

We employed three different questionnaires to assess various aspects of mental health: the Patient Health Questionnaire-9 (PHQ-9)⁵ for depressive symptoms, the General Anxiety Disorder Scale-9 (GAD-7)⁶ for anxiety, and the Karolinska Exhaustion Disorder Scale (KEDS)⁷ for exhaustion.

PHQ-9 consists of nine questions aligned with the diagnostic criteria for major depressive disorder in the DSM-IV⁵. Each question is scored on a scale from 0 (not at all) to 3 (nearly every day), considering the frequency of symptoms over the past two weeks. The total score, ranging from 0 to 27, helps gauge the severity of depression, with higher scores indicating more severe depressive symptoms. The cut-off scores for PHQ-9 are as follows: Minimal depression ranges from 0 to 4, mild depression from 5 to 9, moderate depression from 10 to 14, moderately severe depression from 15 to 19, and severe depression from 20 to 27. A ≥20% reduction from baseline is typically used to indicate a clinically meaningful improvement in depressive symptoms ⁵.

GAD-7⁶ comprises seven questions, each rated on a scale from 0 (not at all) to 3 (nearly every day), reflecting the frequency of anxiety symptoms over the past two weeks. The total score ranges from 0 to 21, with higher scores indicating greater anxiety severity. The cut-off scores for GAD-7 are as follows: minimal anxiety ranges from 0 to 4, mild anxiety from 5 to 9, moderate anxiety from 10 to 14, and severe anxiety from 15 to 21. A 4-point reduction has been suggested as the threshold for minimum clinically important difference (MCID)⁸.

Sleep problems

The Insomnia Severity Index (ISI)⁹ assessed the severity of both nighttime and daytime components of insomnia. It consists of seven items that evaluate the nature, severity, and impact of insomnia over the past two weeks. Each item is rated on a 5-point Likert scale ranging from 0 (no problem) to 4 (very severe problem), with the total score ranging from 0 to 28. Higher scores on the ISI indicate greater severity of insomnia symptoms. The cut-off scores for interpreting the ISI are as follows: scores from 0 to 7 indicate no clinically significant insomnia; scores from 8 to 14 suggest subthreshold insomnia; scores from 15 to 21 reflect clinical insomnia of moderate severity; and scores from 22 to 28 indicate severe clinical insomnia. For ISI, two MCID thresholds have been proposed based on different outcome anchors. A 6-point reduction is commonly used to indicate clinically meaningful

improvement in individuals with primary insomnia ¹⁰. However, smaller changes around 2.5 points have also been associated with meaningful improvements in functioning and mood in non-clinical populations ¹⁰. In this study, we report the proportion of participants meeting both thresholds to provide a range of interpretive perspectives, recognizing the non-clinical nature of our sample.

Health-related quality of life

The RAND-36 was used to measure HR-QoL and includes 36 items that measure eight health domains: physical functioning, role limitations due to physical health problems, role limitations due to emotional problems, energy/fatigue, emotional well-being, social functioning, pain, and general health perceptions. An additional item assesses the change in health the last 12 month and is labelled health transition. Each domain is scored on a scale from 0 to 100, with higher scores indicating better health outcomes ¹¹.

Data analysis

In the quantitative analysis, descriptive statistics were used to summarize participant characteristics, background variables, recruitment, adherence, and satisfaction rates. Categorical data were reported as counts and percentages, while continuous variables were presented as means with standard deviations (SD) or medians with interquartile ranges, depending on the data distribution. To evaluate the limited efficacy of the intervention, Linear Mixed Models (LMM) were applied to data collected at baseline, 6 months, and 12 months. LMM was chosen for its ability to handle repeated measures and missing data, with time treated as both a fixed and repeated effect, an unstructured covariance type, and maximum likelihood estimation ¹². A paired sample t-test was conducted to analyze changes in physical activity between baseline and 12 months. In line with recommendations for feasibility studies by Bowen et al. (2009) ², effect sizes were prioritized to assess limited efficacy and P-values were reported for transparency but were not used to infer significance, as feasibility studies are not powered for hypothesis testing. For each outcome, we reported means, SDs, change scores with 95% confidence intervals (CI), p-values and effect sizes (Cohen's *d*), interpreted using conventional thresholds where 0.20–0.49 indicates a small effect, 0.50–0.79 a moderate effect, and ≥ 0.80 a large effect.

Limited efficacy was treated as an exploratory within group appraisal under Bowen's framework. We summarised the pattern across domains rather than any single measure and flagged a limited efficacy signal when at least three target domains showed a Cohen's *d* of

0.20 or greater at 6 or 12 months. We considered durability to be supported when these changes were maintained or further improved at 12 months. These parameters describe feasibility stage signals and are not hypothesis tests or pass or fail rules. All statistical analyses were performed using IBM SPSS version 25.0.

References

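### If the RAND-36 health-transition item is analysed as change from baseline, the result is a change of a change and does not measure improvement over the massage year

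*Combined protocol and SAP*

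**What the plan says.** The Health-related quality of life section describes the RAND-36 as eight domains plus one further item: "An additional item assesses the change in health the last 12 month and is labelled health transition". For the domains it states: "Each domain is scored on a scale from 0 to 100, with higher scores indicating better health outcomes". It gives no scoring or no-change value for the further item.

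On timing, the Data collection section states: "Data was collected at three time points: baseline, 6 months, and at the end of the massage intervention after 12 months". At 6 months "participants completed the same set of questionnaires as at baseline", and the set was repeated at 12 months.

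On analysis, the Data analysis section states: "Linear Mixed Models (LMM) were applied to data collected at baseline, 6 months, and 12 months". On reporting it states: "For each outcome, we reported means, SDs, change scores with 95% confidence intervals (CI), p-values and effect sizes". The only outcome given a different method is physical activity, which gets a paired t-test. A limited-efficacy signal is flagged when three or more target domains reach a Cohen's d of "0.20 or greater at 6 or 12 months". The target domains are not listed, and the health-transition item is not mentioned anywhere in the section.

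**The concern.** Subtracting baseline makes sense for a measure of current or recent state. The other instruments with a stated recall period are of that kind: the past month for the PSS-10, and two weeks for the PHQ-9, GAD-7 and ISI. The transition item differs because each answer is already a comparison of health now with health a year ago. A baseline-to-follow-up difference in it compares two separate years and does not say whether participants felt better at the end of the massage year than at its start.

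The design is within-group, so no comparator would expose the artefact. At stake is one row of the results table that could be read as a gain or loss in health when participants reported neither. That row might also be counted as a small effect when the pattern across domains is summarised.

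**Working it through.** **Nothing to reproduce.** The plan gives no scoring, SD, expected value or effect size for this item, and the planned 50 participants are stated not to be a powered sample. The check is therefore a reading of the recall windows followed by an illustration on declared assumptions.

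**Recall windows.** Recruitment was planned for November to December 2022, massage ran through 2023, and the last questionnaires came in December 2023 to January 2024.

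| Rating | 12 months it looks back on | Share before massage |
|---|---|---|
| Baseline | roughly 2022 | all |
| 6 months | second half of 2022 and first half of 2023 | about 6/12 = one half |
| 12 months | roughly 2023 | about none |

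**Algebra.** Let *P* be the mean rating of the pre-study year, *M* the mean rating of the massage year, and *c* the no-change value.

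- Reported improvement over the massage year: *M* − *c*.
- Change score from baseline: *M* − *P* = (*M* − *c*) − (*P* − *c*).

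The two agree only if *P* = *c*, that is, if the pre-study year was rated on average as no change.

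**Flat massage year.** Assumptions, none of them in the documents: scoring 0 to 100, *c* = 50, *M* = 50. Then d = (50 − *P*)/SD:

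| *P* | SD 18 | SD 20 | SD 25 |
|---|---|---|---|
| 44 | 6/18 = 0.33 | 6/20 = 0.30 | 6/25 = 0.24 |
| 45 | 5/18 = 0.28 | 5/20 = 0.25 | 5/25 = 0.20 |
| 46 | 4/18 = 0.22 | 4/20 = 0.20 | 4/25 = 0.16 |

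Eight of the nine cells reach 0.20 and one does not. The true massage-year change is 50 − 50 = 0 in all nine.

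**Same check from response distributions.** Further assumptions: steps of 25 points, and 12-month answers of 15% worse, 70% same and 15% better, independent of the baseline answers. The mean is then 50 at 12 months and 50 + 25 × (share better − share worse) at baseline. The plan does not say which SD Cohen's d uses, so the range covers the SD of the change, the baseline SD and the average SD.

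| Baseline worse / better | Baseline mean | Change score | d |
|---|---|---|---|
| 25% / 15% | 47.5 | +2.5 | 0.12 to 0.17 |
| 30% / 15% | 46.25 | +3.75 | 0.18 to 0.25 |
| 40% / 10% | 42.5 | +7.5 | 0.36 to 0.50 |
| 15% / 40% | 56.25 | −6.25 | −0.28 to −0.40 |

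The last row is an apparent deterioration with flat health in the massage year.

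**Hidden gain.** If health improved equally in both years, *M* = *P* > *c*. The change score is 0 although *M* − *c* is positive.

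**6-month rating.** If it blends the two years evenly, its mean with a flat massage year is (*P* + 50)/2. With *P* = 42 the three means are 42, 46 and 50. At SD 20, d is 4/20 = 0.20 at 6 months and 8/20 = 0.40 at 12 months. That would look like a gain that is maintained and growing, with health flat throughout the study.

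**The case against.** The strongest reply is that the plan never says this item gets a change score. The Data analysis section does not name it. The Data collection section lists outcomes by construct, with health-related quality of life among them but not health transition. That stands: the reading rests on a rule stated for every outcome with no exception, so the point is conditional.

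A reader might infer that the item inflates the limited-efficacy signal. The documents do not support that. The item is described as additional to the eight domains, while the signal rule counts target domains. Since those are not listed, the item cannot be ruled out, but nothing places it among them. Even if counted, it would be one of at least three. The plan also says that it looks at the pattern across domains and that its parameters do not decide pass or fail.

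A reader might also infer that the error always flatters massage. It does not: the direction depends on how participants rated the year before, which the documents do not report.

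The illustration uses assumed scoring, SDs and pre-study means, and a mild prior decline stays below 0.20. That also stands.

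Finally, a move from a declining year to a stable one is a change of trajectory that could legitimately be described, and the baseline answers are useful context in an uncontrolled study. That is a reason to show the baseline answers with a clear label. It does not make their subtraction an estimate of improvement during the study.

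**Conclusion.** The point holds in conditional form and is minor. Followed literally, the analysis rule gives the transition item a score that does not estimate improvement over the massage year and can err in either direction. The d range of about 0.16 to 0.33 illustrates how modest a poor pre-study year needs to be; it is not a prediction for this sample. It rests on the assumed scoring, the SDs of 18 to 25, the pre-study means of 44 to 46 and a flat massage year. A pre-study mean above 50 reverses the sign. The logic of the recall windows needs none of these assumptions, only the item's 12-month look-back and the study calendar. No conclusion of the study is shown to turn on this item.

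**What to change.** Add one sentence to the Data analysis section stating that the health-transition item is excluded from the linear mixed model, the change scores, Cohen's d and the limited-efficacy count. Report its 12-month response distribution, or its mean with 95% CI against the no-change category, as participants' direct rating of change over the massage year. State the scoring used. Show the baseline distribution beside it, labelled as describing the year before massage and given as context only. If the 6-month answers are shown, note that about half their recall window precedes the intervention.

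Under this reading, the flat-health scenarios above give 50 − 50 = 0, as they should. No new data are needed, and the cost is one fewer change-score row.

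### Does the limited efficacy flag need a tighter definition of its target domains, its direction and the SD behind Cohen's d?

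*Combined protocol and SAP*

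**What the plan says.** The Study design section describes limited efficacy as "a preliminary within group assessment of the direction and magnitude of change". The Data analysis section turns this into a summary rule: "We summarised the pattern across domains rather than any single measure and flagged a limited efficacy signal when at least three target domains" show a d of 0.20 or more at either follow-up visit. The next sentence treats durability as supported when those changes hold or improve further by 12 months. The section then says that these parameters are neither hypothesis tests nor pass/fail rules. It gives effect sizes priority over p-values and reports means, SDs, changes with 95% confidence intervals, p-values and d for each outcome.

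The Data collection section lists the baseline outcome variables as "stress, mental health, sleeping problems, physical activity, HR-QoL and work ability". Its 6-month list is shorter, "as well as questions about stress, mental health, sleep problems, HR-QoL, and work ability", and leaves out physical activity. Under Mental Health: "We employed three different questionnaires to assess various aspects of mental health". Under Health-related quality of life, the RAND-36 "includes 36 items that measure eight health domains". The scales do not all run the same way. For insomnia, "Higher scores on the ISI indicate greater severity of insomnia symptoms", while the RAND-36 domains are scored "with higher scores indicating better health outcomes".

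**The concern.** The rule has a numerical threshold and a numerical count, yet the thing counted is not defined. Target domains could be the six outcome variables in the Data collection section. The word domain is otherwise used for the eight RAND-36 scores, so a reader could also count individual scales. Even on the six-variable reading, it is not stated whether one scale at 0.20 is enough for mental health (three scales) or health-related quality of life (eight scores).

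The SD for d is not named. In a pre-post design the baseline SD and the SD of change can put the same result on different sides of 0.20. One threshold also covers effect sizes from two analyses, the mixed model and the paired t-test for physical activity. The flag sentence carries no sign, although the scales run in opposite directions.

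At stake is whether two careful readers with the same results would agree that a signal was flagged, in a study meant to inform a later powered trial. The document is dated 2025-10-17, after the last data collection in December 2023 to January 2024, so which version was applied matters to a reader.

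**Working it through.** The plan states no power, error rate or operating characteristic for the flag, so there is no figure to reproduce. The check asks which points the text settles, and how much the remaining ones can move the flag.

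**Points the text settles**

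- *Direction.* Study design defines limited efficacy by direction as well as size. The durability sentence refers back to the flagged changes and speaks of further improvement. The scoring direction is given for PSS-10, PHQ-9, GAD-7, ISI and RAND-36. Counting improvement only is the natural reading, and at most a sign convention is unstated.
- *Physical activity.* It is absent from the 6-month list, and its paired t-test compares baseline with 12 months. It can count only at 12 months.

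**Inputs for the open points**

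- From the documents: threshold 0.20, at least three domains, 6 or 12 months, planned n = 50, six variables.
- Scores: 1 stress + 3 mental health + 1 sleep + 1 physical activity + 8 RAND-36 + 1 work ability = 15. One score each for physical activity and work ability is assumed.
- Also assumed: normal data, equal SDs over time, between-scale correlation 0.5, retest correlation r = 0.5, 0.6 or 0.7, and the same true change on every scale.

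**Choice of SD**

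d(change SD) = d(baseline SD) / √(2(1 − r)).

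- r = 0.5: factor 1/√1.0 = 1.00
- r = 0.6: factor 1/√0.8 = 1.12
- r = 0.7: factor 1/√0.6 = 1.29

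At r = 0.7, a d of 0.20 on the change SD is 0.20 × √0.6 = 0.155 on the baseline SD. For one scale at one visit with no true change, P(d ≥ 0.20) is 1 − Φ(0.20 × √50) = 1 − Φ(1.414) = 0.079 on the change SD. On the baseline SD at r = 0.7 it is 1 − Φ(1.414/√0.6) = 1 − Φ(1.826) = 0.034.

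**Flag rates on the six-variable reading**

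These come from simulation with 50,000 replicates per cell, counting improvement only. A multi-scale variable counts if one scale reaches 0.20 (one), or if 2 of 3 mental health scales or 5 of 8 RAND-36 scores do so at the same visit (most). Entries are for r = 0.5 / 0.6 / 0.7.

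| Version | No true change | 0.1 SD improvement |
|---|---|---|
| one, baseline SD | 20% / 14% / 8% | 54% / 50% / 44% |
| most, baseline SD | 8% / 5% / 2% | 33% / 29% / 24% |
| one, SD of change | 20% / 20% / 20% | 55% / 60% / 66% |
| most, SD of change | 8% / 8% / 8% | 33% / 38% / 45% |

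Share of studies in which the four versions do not all agree:

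| True improvement on every scale | r = 0.5 | r = 0.6 | r = 0.7 |
|---|---|---|---|
| none | 15% | 15% | 17% |
| 0.1 SD | 28% | 32% | 42% |
| 0.2 SD | 19% | 20% | 23% |
| 0.3 SD | 5% | 4% | 3% |

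At 0.1 SD, the counting rule alone (baseline SD) accounts for 21% / 21% / 20%, and the SD alone (one scale enough) for 7% / 11% / 22%. Counting all 15 scores separately, instead of six variables, raises the no-change flag rate from 20% / 14% / 8% to 29% / 22% / 13% (one scale enough, baseline SD).

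**What a reader can recover**

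The change, its confidence interval and the visit SDs are reported for each outcome. The SD of change is about (half-width of the interval) × √n / t, with t the 97.5% quantile. Dividing the change by this SD and by the baseline SD, and comparing with the reported d, usually shows which was used. The match is close for the paired t-test and approximate for the mixed model when visits are missing. Where the two cannot be told apart, they give nearly the same d and the choice is immaterial.

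**The case for a change.** The strongest case for a change is that being exploratory excuses the absence of error control but does not excuse an undefined number. The plan puts effect sizes ahead of p-values, so the definition of d is central. A reader who recounts the domains still cannot be certain which version the authors applied. A few sentences would settle it and need no new data.

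Part of this stands. Neither the within-domain counting rule nor the SD is written down, and the six-variable reading is an inference that the text supports but does not state. A good report would name the SD and the scales behind any flag.

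The step from there to a change of plan does not stand. The rule is reported in the past tense after data collection, so new wording cannot pre-specify anything. A domain list supplied from outside could misdescribe what was done. Nor is there a clearly better rule to adopt. Letting one scale suffice raises the no-change flag rate from 8% / 5% / 2% to 20% / 14% / 8% on the baseline SD. It also lets quality of life count in 47% / 39% / 28% of null studies, against 14% / 10% / 6.5% for stress. Requiring most scales lowers the flag rate at a 0.1 SD improvement from 54% / 50% / 44% to 33% / 29% / 24%. The SD choice is a similar trade-off between the spread of the population and the precision of within-person change.

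**Conclusion.** No change to the plan follows. Two definitions are missing from the description of the flag: how a multi-scale domain counts, and which SD divides the change. The list of domains has to be inferred. Direction and the single follow-up for physical activity can be read from the text.

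Following the plan gives no wrong estimate, interval or decision. The flag carries no error rate and is expressly not a pass/fail criterion, and the d, SD and interval of each outcome are reported beside it. The four versions fail to agree in 15% to 17% of studies with no true change, in 28% to 42% at 0.1 SD, and in 3% to 5% at 0.3 SD. The largest figures combine two choices at a small uniform change. All of them rest on n = 50, normal data, a between-scale correlation of 0.5 and retest correlations of 0.5 to 0.7; except for the planned n, none of these is in the documents. They measure how far readings can differ and say nothing about the study's actual result. This is a gap in reporting detail that the analysts can fill sensibly when they present the effect sizes.
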